Analysis approach

Statistical analysis will be performed by Stata, version 15. The baseline characteristics will be assessed by arm. The primary analysis will be an intention-to-treat (ITT) analysis. We will compare the mean length velocity (cm/ month) (primary outcome), weight velocity (gm/kg/day), LAZ, WLZ, and WAZ between the two intervention arms and the control arm using ANOVA, with the model adjusted for the birth weight and age of the infants at enrollment. If an outcome is missing for the intention-to-treat infants, the means from that group will be imputed.

Safety outcomes

i. Maternal serious adverse events

The occurrence of maternal SAEs will be expressed as the proportion of women with at least one SAE during the follow-up period (from enrolment to 179th day). The proportion will be calculated by dividing the number of women with at least one recorded SAE by the total number of enrolled participants. Results will be shown both as proportions of participants with any SAE as well as tabulated by the SAE category (death, hospitalization, other). If any participant has experienced more than one type of SAE, the participant will be recorded in each category.

ii. Infant serious adverse events

The occurrence of infant SAEs will be expressed as the proportion of babies with at least one SAE during the follow-up period (from enrolment to 179th day). The proportion will be

calculated by dividing the number of babies with at least one recorded SAE by the total number of recorded newborns. Results will be shown both as proportions of participants with any SAE as well as tabulated by the SAE category (death, hospitalization, other). If any participant has experienced more than one type of SAE, the participant will be recorded in each category.

Interim analysis

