11. SAMPLE SIZE CALCULATIONS & POWER ANALYSIS

The sample size is calculated and powered to look at multiple comparisons, between arms A and B, A and C plus B and C with a hypothesized higher increase with addition of Azithromycin to infant with Afzaaish in LW. Also, adjustment for multiple comparison is needed. Thus, calculations for the sample size is estimated and are per arm sample size is provided below based on the primary outcome of length velocity in LW trial with 1-sided testing, alphas to account for multiple comparison (the lower alpha), and drop out of 14% is assumed in the trial.

Assumptions for Sample Size Calculations

Variable	Difference	Std Dev	Alpha	Drop out portion	n/arm	n/arm adj dropout	Actual Power
Length Velocity	0.12	0.5	0.025	0.14	274	319	0.801

Based on assumptions, a sample size of 319 children per arm is calculated, assuming 14% drop out rate (i.e. 10% margin for loss to follow up, and 4% infants deaths).

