This is a community-based, open-label, multiarm randomized controlled trial that will include parallel group assignments with a 1:1:1 allocation ratio in low-income squatter settlements in urban Karachi, Pakistan. The women in the control group (control arm) will receive standard counseling only, whereas the lactating women in the first intervention group (intervention arm 1) will receive two sachets of balanced energy-protein (BEP) supplementation per day from enrollment until the infant reaches six months of age. The lactating women in the second intervention group (intervention arm 2) will receive the same BEP supplementation as those in intervention arm 1 while their babies will also receive a single stat dose (20 mg/kg orally) of Azithromycin at 42 days.

2. Objectives

The primary objective is to compare the efficacy of fortified, balanced energy-protein (BEP) supplements being consumed by lactating women for 6 months (intervention arm 1) with or without a single prophylactic dose of oral azithromycin to the infant at 42 days of age (intervention arm 2) with that of standard exclusive breastfeeding and nutritional counseling alone (control arm) in improving length velocity among infants at 6 months (outcome). The secondary outcome is to compare the impact of the interventions on weight (or growth) velocity, Z-scores, other anthropometry measures of infants, maternal weight changes, breast milk quality, gut microbiota, and key micronutrient levels in both the mother and infant.

3. Study setting and study population

The trial is being conducted in the peri-urban communities of Karachi, Pakistan. The study population includes only lactating women of reproductive ages who have recently delivered and their infants. Lactating women between 13 and 49 years of age and their newborns are the study population.

4. Primary hypothesis

Length velocity at 6 months of infant's age

H_a = Mean difference in length velocity of $>0.12\text{cm/month}$ to look at comparisons between multiple arms

H_o = Mean difference in length velocity of $\leq 0.12\text{cm/month}$ to look at comparisons between multiple arms

5. Secondary hypothesis

Growth velocity at 6 months of infant's age

H_a = Mean difference in growth velocity of $>0.4\text{ gram/kg/day}$ to look at comparisons between multiple arms

H_o = Mean difference in growth velocity of $\leq 0.4\text{ gram/kg/day}$ to look at comparisons between multiple arms

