The null hypothesis for this trial is that the mean difference in length velocity between an infant of a lactating woman receiving standard breastfeeding counseling with BEP alone (Intervention arm 1) for 6 months or in combination with a single prophylactic dose of azithromycin at 42 days of age (Intervention arm 2) and an infant of a lactating woman receiving standard breastfeeding counseling alone (control arm) is equal or less than 0.12 cm/month (primary outcome). Due to the absence of evidence of such interventions on length velocity, we based this hypothesis on our local experience and field data from our field sites. The alternate hypothesis for this trial is that an infant of a lactating woman receiving BEP alone for 6 months or in combination with a single prophylactic dose of azithromycin at 42 days of age has a mean length velocity is greater than 0.12 cm/month that of an infant of a lactating woman not receiving an intervention at 6 months. The sample size takes multiple comparisons into account and is based on the primary outcome of length velocity with an effect size of difference of 0.12 cm per month between the arms (i.e., 0.72 cm difference at 6 months), a 1-sided test, power of 80% and an alpha of 0.025 to account for multiple comparisons (the lower alpha – Bonferroni correction was used). A drop-out rate of 14% (i.e., 10% loss to follow up and infant mortality rate of 4%) is assumed in the study, so the minimum total sample size required is 957 (319 lactating women in each arm).

7. Eligibility criteria

Inclusion Criteria

- a) Lactating women with a mid-upper-arm-circumference (MUAC) of < 23.0 cm
- b) Infants with a live birth outcome, captured within 168 hours (0-6 days)
- c) Individuals with the intention to stay in the catchment area for entire duration of trial after enrollment
- d) Individuals with the intention to exclusively breastfeed child for at least 6 months of age
- e) Individuals who have provided voluntary written informed consent

Exclusion Criteria

- a) Newborns with a birth weight of less than 1500 grams
- b) Newborns with a known congenital anomaly or other severe illness based on the study physician's assessment before enrollment.
- c) Lactating women with known allergies to peanut, lentils, chickpea or dairy products
- d) Individuals who were previously enrolled in the trial

8. Blinding

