The primary analysis will be by intention-to-treat (ITT) perform for those who had anthropometry at 6 months. All analyses will be done using Stata software version 16. The WHO 2009 Child Growth Standards will be used for age-sex standardization of child length, weight, head circumferences, MUAC and weight-for-height. Descriptive analysis of each arm will be conducted, and percentages or continuous data with SD will be reported.

The baseline characteristics will be assessed by arm. Outcomes of mean length velocity, growth velocity, weight gain, z scores and change in z score from 0-6 month will be compared using one way analysis of variance (ANOVA). Tukey's test will be used for multiple comparisons. As determined *a priori* the analysis will be adjusted for the birth weight and length of infant, maternal MUAC at enrollment, maternal age, gravida, maternal body mass index and gender of child using general linear model (GLM). Mixed model analysis will be used to compare change in outcome per month in the intervention arm compared to the control arm. Using repeated measures ANOVA, the analysis will report beta coefficients and 95% CI. The coefficients represents the rate of change in outcome per month. For covariate adjustment, an unadjusted and stepwise adjusted model will be run. Trajectories will be plotted for mean length and weight by age for each arm, and monthly z scores were also be plotted.

13. Potential sub-group analysis

The following variables will be considered for sub-group analysis for primary and secondary outcomes:

1. Birth weight i.e. <2500 gm and => 2500 gm
2. Maternal MUAC at enrolment i.e. < 21.0 cm and =>21.0 cm
3. Maternal age i.e. <30 years and => 30 years
4. Gravidity i.e. <3 and =>3
5. Maternal BMI i.e. <18.5 kg/m² and =>18.5 kg/m²
6. Gender of child

14. Missing Data

We will treat missing data as it is, no imputation will be applied. We discussed that due to growth flattering during this age, imputation maybe unreliable.

15. Interim analysis

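### The 80% power belongs to a one-sided 0.025 t test; the planned Tukey test gives about 68% per pair (at an assumed 5% family-wise level), and the documents disagree on which comparisons count

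*SAP*

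**What the plan says.** **Sizing.** SAP section 6 specifies "a 1-sided test, power of 80% and an alpha of 0.025 to account for multiple comparisons" and adds that "the lower alpha – Bonferroni correction was used". Protocol section 11 agrees: "with 1-sided testing, alphas to account for multiple comparison (the lower alpha), and drop out of 14% is assumed in the trial". Its table gives difference 0.12 cm/month, SD 0.5, alpha 0.025, 274 per arm, 319 after dropout, and power 0.801.

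**Final test.** SAP section 12 compares the arms by one-way ANOVA and then says "Tukey's test will be used for multiple comparisons". It gives neither sidedness nor a family-wise level. It also says "the analysis will be adjusted for the birth weight and length of infant, maternal MUAC at enrollment" and for further baseline variables, in a general linear model.

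**Comparison family.** Protocol section 11 says the sample size is powered for comparisons "between arms A and B, A and C plus B and C with a hypothesized higher increase with addition of Azithromycin". Protocol section 10 (Analysis approach) compares outcomes "between the two intervention arms and the control arm using ANOVA". The SAP section 2 objective and the SAP section 6 null also set the intervention arms against control only. SAP section 4 speaks loosely of multiple arms, and SAP Table 3 has a pairwise-comparison column; neither says which pairs are confirmatory.

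**The concern.** Power is a property of a particular test. If the sizing test and the final test differ in sidedness, number of comparisons and critical value, the stated 80% does not describe the analysis that will be run.

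The family matters as well. A Bonferroni split of one-sided 0.05 gives 0.025 for two comparisons but 0.0167 for three. The stated alpha therefore suits the two control comparisons and not the three-pair claim in Protocol section 11.

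Two things are at stake: an overstated chance of detecting the planned effect, and a primary result whose success could depend on which section is followed. A t statistic between 1.96 and 2.35 passes under SAP section 6 and fails under SAP section 12.

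**Working it through.** **Inputs.** Difference 0.12, SD 0.5, one-sided alpha 0.025, dropout 14%, 274 evaluable per arm (Protocol section 11; all but the SD and the 274 are also in SAP section 6). The null is zero difference, as the sizing implies. SAP section 12 analyses only infants with 6-month anthropometry and section 14 applies no imputation, so 274 is the planning number.

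**1. Reproduce the plan's figure.**
- Standard error = 0.5 × √(2/274) = 0.0427. Noncentrality = 0.12/0.0427 = 2.809.
- One-sided 0.025 t test, critical value 1.96: power 0.8007 at 274 (0.7993 at 273).
- 274/0.86 = 318.6, so 319 per arm; 3 × 319 = 957.

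The arithmetic is right for that test. An unadjusted two-sided 5% test has the same critical value.

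**2. Power of the planned test.** Tukey's critical value is the studentized range quantile for 3 groups and 3 × 273 = 819 degrees of freedom, divided by √2. Power is from the noncentral t distribution.

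| Family-wise level (assumed) | Critical value | Power per pair, 274 per arm |
|---|---|---|
| 2.5% | 2.610 | 57.9% |
| 5% | 2.348 | 67.8% |
| 10% | 2.055 | 77.4% |

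At 5%, power would be 75.3% even if all 319 per arm were evaluable. With 274, the difference detectable with 80% power is about 0.136 cm/month. Reaching 80% per pair for 0.12 would take 354 evaluable per arm: 354/0.86 = 411.6, so 412 randomised and 1,236 in total, against 957.

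As observed differences, the thresholds are 1.96 × 0.0427 = 0.084 and 2.348 × 0.0427 = 0.100 cm/month.

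**3. Covariate adjustment.** If covariates explain a share R² of the variance, the noncentrality becomes 2.809/√(1 − R²). Tukey power at 5% is then:

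| Assumed R² | Power per pair |
|---|---|
| 0.10 | 73.0% |
| 0.15 | 75.8% |
| 0.20 | 78.6% |
| 0.30 | 84.3% |

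It reaches 80% at R² of about 0.22. The documents give no R² and credit no gain.

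**4. Both control comparisons together** (both intervention arms truly 0.12 above control; simulation):

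| | Tukey, 5% | One-sided 0.025 each |
|---|---|---|
| At least one significant | 82.6% | 91.3% |
| Both significant | 52.9% | 68.8% |
| Neither significant | 17.4% | 8.7% |

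**5. Other coherent choices, 274 per arm, power per comparison.**
- Two control comparisons: one-sided 0.025 each, 80.1%; one-sided Dunnett (critical value 1.914), 81%; two-sided Dunnett (2.215), 72%.
- Three pairs, one-sided Bonferroni at 0.05/3 = 0.0167: 75.0%.

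The one-sided family-wise error at 0.025 per test is about 4.5% for the two control comparisons and 6.5% for three pairs. The SAP does not plan the latter procedure.

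**The case against.** The strongest reply has four parts.

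- **The 5% level is assumed.** Bonferroni 0.025 for two comparisons implies an overall one-sided 5%, whose two-sided counterpart is 10%. Tukey at 10% gives 77.4%, so only 80.1 − 77.4 = 2.7 points come from using Tukey over three pairs; the other 77.4 − 67.8 = 9.6 come from the assumed level. This decomposition is fair. But 5% is the usual default, the SAP states no other, and none of the three levels reaches 80% unadjusted.
- **80% could mean at least one success.** The SAP's alternative is worded with *or*, and if both arms work Tukey finds at least one control difference 82.6% of the time. The sizing, however, is a two-arm calculation for one comparison, and on the at-least-one measure its test would score 91.3%.
- **Tukey on unadjusted means may not be decisive.** SAP section 12 also plans an adjusted model and a mixed model against control, and Protocol section 10 adjusts too. Baseline length is both a covariate and part of the outcome, so zero gain is the pessimistic end. That stands as a caution about the 68%. It also confirms that the decisive test is not named.
- **80% can be kept with three two-sided comparisons.** A fixed sequence at two-sided 5% controls the family-wise error and leaves B–C confirmatory. It does, but keeps 80% only for the first test; later steps have less.

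It is also true that the sample-size arithmetic contains no slip and that Tukey does not inflate false positives.

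**Conclusion.** The concern holds. The stated 80% is correct for a one-sided 0.025 t test and not for the planned Tukey comparison, whose power is 67.8% per pair. That figure rests on a true difference of 0.12, SD 0.5, 274 evaluable per arm, a zero null, an assumed 5% family-wise level and no covariate gain. The range is 57.9% to 77.4% over family-wise levels of 2.5% to 10%, and 73.0% to 84.3% at the 5% level if covariates explain 10% to 30% of variance.

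Separately, the documents conflict on whether the family has two or three comparisons, and no section fixes family, sidedness and family-wise level for the final test. The trial remains valid. This should be fixed because the power claim and the primary decision rule do not match the analysis.

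**What to change.** State one family, one sidedness and one family-wise alpha in both documents, name the decisive model, and restate power for it. Two coherent routes:

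- **Three pairs confirmatory.** Suggested text: *A–B, A–C and B–C; two-sided; family-wise 5%; Tukey; power about 68% per pair for 0.12 cm/month (SD 0.5, 274 evaluable of 319 randomised per arm, no covariate gain assumed).* Delete the one-sided 0.025 Bonferroni wording.
- **Two control comparisons confirmatory.** For the primary outcome, replace Tukey with one-sided 0.025 per comparison (80%) or two-sided Dunnett (72%). Make B–C secondary and remove it from the power claim in Protocol section 11.

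A closed procedure gated by the overall F test is a further option for three arms. Its per-pair power was 0.70 to 0.80 in the configurations checked, but it gives up simultaneous confidence intervals. A fixed sequence is also possible, with power stated for each step.

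The cost is wording only, with no added enrolment. Keeping Tukey means reporting a less favourable power; keeping 80% for both control comparisons means giving up confirmatory B–C and two-sided testing. The choice must be made and dated before unblinding, because moving from Tukey to one-sided 0.025 lowers the critical value from 2.35 to 1.96.

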10.1. Primary growth outcome*

- **'Length velocity (cm/month) of infant'** at 6 months is define as = $(\text{Length at 6-month visit} - \text{Length at baseline}) / (\text{Date of visit of visit at 6-month} - \text{Date of enrollment}) * 30.4$. (3)

10.2. Secondary growth outcomes*

- **'Growth velocity (gm/kg/day) of infant'** at 6 months is define as per Patel Exponential method = $[1000 \times \ln(\text{Weight at 6-month visit} - \text{Weight at baseline})] / (\text{Date of visit of visit at 6-month} - \text{Date of enrollment})$. (4)
- **'Weight gain (gm/month) of infant'** at 6 months is define as = $(\text{weight at 6-month visit} - \text{weight at baseline}) / (\text{Date of visit of visit at 6-month} - \text{Date of enrollment}) * 30.4$.
- **'LAZ, WAZ and WLZ of infant'** at 6 months is define as per WHO z-anthro 2006 guidelines and standard queries. Change in
- **Stunting** at 6-month is define as <-2 SD length for age z score
- **Wasting** at 6-month is define as <-2 SD weight for length z score
- **Underweight** at 6-month is define as <-2 SD weight for age z score
- **'Gain in infant MUAC (cm/month)'**, at 6 months is define as = $(\text{MUAC at 6-month visit} - \text{MUAC at baseline}) / (\text{Date of visit of visit at 6-month} - \text{Date of enrollment}) * 30.4$
- **'Gain in infant head circumference (cm/month)'**, at 6 months is define as = $(\text{head circumference at 6-month visit} - \text{head circumference at baseline}) / (\text{Date of visit of visit at 6-month} - \text{Date of enrollment}) * 30.4$
- **'Maternal weight change Kg/month'**, at 6 months is define as = $(\text{Maternal weight at 6-month visit} - \text{Maternal weight at baseline}) / (\text{Date of visit of visit at 6-month} - \text{Date of enrollment}) * 30.4$
- **'Gain in Maternal MUAC (cm/month)'**, at 6 months is define as = $(\text{MUAC at 6-month visit} - \text{MUAC at baseline}) / (\text{Date of visit of visit at 6-month} - \text{Date of enrollment}) * 30.4$

*All measurements were taken at baseline, then day 27, 56, 89, 114, 143 and 177-179 of infant's age. we allow a window until next follow-up is appeared.

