 H_o = Mean difference in WAZ ≤ 0.5 to look at comparisons between multiple arms
 - iv. **Weight-for-Age Z-score of (WAZ) at 6 months of infant's age**
 H_a = Mean difference in WAZ >0.5 to look at comparisons between multiple arms
 H_o = Mean difference in WAZ ≤ 0.5 to look at comparisons between multiple arms

Data cleaning and procedures

Data cleaning process will be done by these procedures:

1. Data analyst will clean the required data for the main analyses. At this point, all investigators will be blinded to the intervention each participant has been receiving.
2. The study statisticians will review the data and complete preliminary analyses for group comparisons (without knowing the actual interventions).

Definition of key variables

- i. **Length velocity**
 Length velocity to be calculated from baseline length measurement of the infants taken within 0-6 days of life and subsequent measurement in 'cm' taken at each 4 weeks interval, until the age of 6 month, calculated as cm/month.
- ii. **Growth velocity**
 Growth velocity to be calculated from baseline weight measurement of the infants taken within 0-6 days of life and subsequent measurement in 'gram' taken at each 4 weeks interval, until the age of 6 month, calculated as gm/kg/month.
- iii. **Length-for-Age Z-score (LAZ) at 6 months of infant's age**
 Length-for-age will be calculated from age, sex, and length information from the baseline measurements within 0-6 days of birth and infant anthropometry on monthly basis until 6

months of age by using the STATA WHO packages using the WHO 2006 multi-centre growth standard. The values will be expressed as Z-score units, with two decimals.

iv. Weight-for-Length Z-score (WLZ) at 6 months of infant's age

Weight-for-length will be calculated from sex, weight and length information from the baseline measurements within 0-6 days of birth and infant anthropometry on monthly basis until 6 months of age by using the STATA WHO packages using the WHO 2006 multi-centre growth standard. The values will be expressed as Z-score units, with two decimals.

v. Weight-for-Age Z-score of (WAZ) at 6 months of infant's age

Weight-for-Age will be calculated from weight, sex and gender information from the baseline measurements within 0-6 days of birth and infant anthropometry on monthly basis until 6 months of age by using the STATA WHO packages using the WHO 2006 multi-centre growth standard. The values will be expressed as Z-score units, with two decimals.

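### SAP 10.2 takes the log of the weight difference instead of the weight ratio, so the printed growth-velocity formula does not give g/kg/day

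*SAP*

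**What the plan says.** SAP section 10.2 lists "Growth velocity (gm/kg/day) of infant" first among the secondary growth outcomes and says that it "at 6 months is define as per Patel Exponential method". The numerator is then printed as "1000 \times \ln(\text{Weight at 6-month visit} - \text{Weight at baseline", with the bracket closing after the baseline weight. The denominator is the number of days from enrolment to the 6-month visit. Neither document gives any other formula for this outcome.

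The outcome carries a hypothesis of its own in SAP section 5: "Mean difference in growth velocity of $>0.4\text{ gram/kg/day}$ to look at comparisons between multiple arms". The same threshold stands in Protocol sections 5, 7.2 and 10, and the outcome has a row in the SAP's results table (Table 3).

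The Protocol is not consistent about the time unit. Under the definition of key variables in section 10 it has "subsequent measurement in 'gram' taken at each 4 weeks interval, until the age of 6 month, calculated as gm/kg/month". The analysis approach in the same section has "weight velocity (gm/kg/day), LAZ, WLZ, and WAZ between the two intervention arms and the control arm using ANOVA".

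**The concern.** If weight grows exponentially, W6 = W0 × exp(k × days), so the rate is k = ln(W6/W0)/days. Multiplied by 1000 this is in g/kg/day. The SAP instead takes the log of W6 − W0, the absolute gain. That is a different quantity and does not match the label.

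The SAP is the only document with a formula to code from, and the final analysis is to be run by a blinded analyst. If the text were followed literally, the arm means and arm differences for this outcome would be wrong in the final report. They would also be wrong at the interim analysis, where secondary outcomes go to the DSMB and a benefit on a secondary outcome is among the grounds for recommending termination or modification.

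**Working it through.** **Inputs.** The printed formula, the g/kg/day label and the 0.4 threshold come from the SAP. Enrolment falls on day 0–6 of life and the last visit on day 177–179. The documents give no expected infant weights, so the weights below are assumptions chosen for illustration. There is no stated mean or power figure for this outcome to reproduce.

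**Forms compared.** Printed: 1000 × ln(W6 − W0)/days. Ratio: 1000 × ln(W6/W0)/days.

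**1. Values over 177 days**

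| Assumed infant | Printed, grams | Printed, kg | Ratio (g/kg/day) |
|---|---|---|---|
| 2.8 → 7.0 kg | 1000·ln(4200)/177 = 47.13 | 1000·ln(4.2)/177 = 8.11 | 1000·ln(7.0/2.8)/177 = 5.18 |
| 2.0 → 6.0 kg | 46.86 | 7.83 | 6.21 |
| 3.5 → 7.7 kg | 47.13 | 8.11 | 4.45 |

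The 2.0 → 6.0 kg infant ranks lowest on the printed form and highest on the ratio form.

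**2. Unit check.** Going from grams to kilograms shifts the printed value by 1000 × ln(1000)/177 = 39.0. A rate in g/kg/day cannot depend on the unit in which weight was recorded. The ratio form does not.

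**3. Per-kg check.** A gain of 4.2 kg from 2.0, 2.8 or 3.5 kg gives 47.13 each time as printed (grams). The ratio form gives 6.39, 5.18 and 4.45.

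**4. Effect on a difference.** Add 200 g at 6 months. In either weight unit, the printed form changes by 1000 × ln((gain + 200)/gain)/177 and the ratio form by 1000 × ln((W6 + 200)/W6)/177, with gain and W6 in grams here.

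| Infant | Printed | Ratio | Printed / ratio |
|---|---|---|---|
| 2.8 → 7.0 kg | 0.263 | 0.159 | 1.65 |
| 2.0 → 6.0 kg | 0.276 | 0.185 | 1.49 |
| 3.5 → 7.7 kg | 0.263 | 0.145 | 1.81 |

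**5. What 0.4 means on each scale.** Over 177 days, exp(0.4 × 177/1000) − 1 = 0.0734. As printed, 0.4 corresponds to 0.0734 × gain: 308, 293 and 308 g. By ratio it corresponds to 0.0734 × W6: 514, 440 and 565 g. The shortfall is the fraction W0/W6: 40%, 33% and 45%.

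**6. Sensitivity to the assumed weights.** More extreme pairs widen the range in steps 4 and 5. For 1.5 → 6.0 kg the multiplier is 1.33 and the shortfall 25%. For 3.5 → 6.5 kg they are 2.13 and 54%.

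**7. Interval.** Moving from 179 to 171 days raises every version by the same 4.7% (179/171). Because the printed values are larger, the absolute movement for the 2.8 → 7.0 kg infant is 2.18 (grams) or 0.38 (kg), against 0.24 by ratio. The gram-or-kilogram choice therefore cancels between arms only if their intervals are alike.

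**The case against.** The strongest reply is that this is a typing slip. The method is named and cited, the unit is given, and the neighbouring outcomes all use the same 6-month-minus-baseline template, so the numerator was probably pasted. A programmer who knows the method would write the ratio, and nothing in the documents shows that the code is wrong. This stands as a limit on the likely harm. It does not make the text correct, since a SAP is meant to fix derivations in advance.

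Other points also have some force:

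- **Weight unit.** The SAP's kilogram entry is only a display unit in a baseline table. The Protocol's definition and the SAP's weight gain in g/month both suggest grams. Real ambiguity over the unit is therefore modest, but the unit check still shows that the formula is not a g/kg/day rate.
- **Baseline weight.** Randomisation, and adjustment for birth weight in both analysis sections, soften the loss of standardisation when arms are compared. Neither restores the scale.
- **Illustrative weights.** The multipliers rest on assumed infants, as the wider range in step 6 shows. The defect itself does not depend on them.
- **Text extraction.** A PDF reading error cannot be wholly ruled out, although the minus sign and the bracket around both weights are clear.

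**Conclusion.** The concern holds. The printed formula is not a g/kg/day rate: it depends on the weight unit and is not standardised to baseline weight. This follows from the algebra alone and needs neither the cited paper nor any assumed weights.

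The size does rest on assumed weights. For the three main examples over 177 days, an arm difference would be overstated by a factor of about 1.5 to 1.8, and 0.4 would correspond to 33–45% less weight than intended. No changed decision is claimed, because neither analysis section describes a test against 0.4. The consequence is a reported difference that could not be read against that hypothesis.

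The problem is confined to one secondary outcome. Length velocity, weight gain in g/month, the z-scores and the sample size are untouched. It should be fixed. The Protocol's per-month unit is a separate, smaller slip in the same outcome's definition.

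**What to change.** - **SAP 10.2:** replace the formula with 1000 × ln(weight at 6-month visit / weight at baseline) / (date of 6-month visit − date of enrolment), and state that both weights are in the same unit. The denominator stays as it is.
- **Protocol section 10, growth velocity definition:** change the unit from per month to per day, to match the hypotheses and the analysis approach.
- **Programs:** confirm that the interim and final derivation code uses the ratio form.

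The cost is one line in the SAP, one word in the Protocol and a code check. No new data are needed.
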